9.2 Toxicity Definitions

All study toxicities will be graded by the NCI Common Terminology Criteria for Adverse Events Version 4.0.

10.0 Criteria for Termination

10.1 Conditions for Terminating the Study

The Principal Investigator may terminate the study for any of the following reasons:

- Significant toxicities: Patients with any grade 3/4 toxicity that persists and does not improve 21 days after discontinuation of all study medications, despite pharmacologic management, will be removed from the study. Any patient who experiences any grade 4 toxicity can be removed from the study at the discretion of the study investigator.
- If it becomes clear that the study treatment is less effective than standard treatment. The phase II study has a two-stage design (see section 3 for more details). If fewer than 8 out of the first 20 pts are progression-free at 12 weeks, this would be considered an unacceptably low PFS rate (<39%), the study will not continue and accrual will cease. Study accrual will continue while efficacy is being determined. Conversely, if at least 7 patients in the first stage of the phase II study are free of progressive disease at 12 weeks, then enrollment will continue to the second stage of the study. .
- Once all data collection has been completed.

10.2 Conditions for Individual Patient Termination

The Principal Investigator may terminate the participation of an individual patient for any of the following reasons:

- Disease progression
- Need for exclusionary concurrent treatment
- Withdrawn consent
- Protocol non-compliance
- Lost to follow-up

11.1 Eribulin mesylate (E7389)

11.1.2 Classification

Eribulin mesylate (E7389) is a synthetic analog of Halichondrin B (HalB), a natural product isolated from the marine sponge *Halichondria okadai*.¹ HalB is a large polyether macrolide that exerts potent anticancer effects in cell-based and animal models of cancer. The structurally simplified synthetic analog eribulin mesylate (E7389) encompasses the biologically active macrocyclic portion of HalB, and shows similar or identical anticancer properties in preclinical models.

11.1.3 Mode of Action

E7389 exerts its antiproliferative effects via a tubulin-based antimetabolic mechanism. Currently-available data indicate that its mechanism of action is similar or identical to that of HalB.^{4,5} Like HalB, E7389 was shown to be a potent inhibitor of tubulin polymerization into microtubules as well as microtubule dynamics in vitro and in whole cells.^{4,6} Nonclinical data show that sub- to low-nmol/L levels of E7389 inhibit cancer cell proliferation via induction of irreversible cell cycle blocks at G2/M, disruption of mitotic spindles, and initiation of apoptosis.

Eribulin inhibits the growth phase of microtubules without affecting the shortening phase and sequesters tubulin into nonproductive aggregates. Eribulin exerts its effects via a tubulin-based

antimitotic mechanism leading to G2/M cell-cycle block, disruption of mitotic spindles, and, ultimately, apoptotic cell death after prolonged mitotic blockage.

11.1.4 Storage and Stability

The long-term storage condition for E7389 drug product is to store at 2°C to 8°C (do not freeze). Clinical supplies labeled for storage at temperatures up to 25°C have been reassigned to refrigerated storage (2°C to 8°C) to provide an extended provisional shelf life.

The drug product may be administered without dilution or diluted with 0.9% Sodium Chloride Injection to concentrations between 0.005 mg/mL and 0.2 mg/mL, and administered per Eisai's directions.

Photostability studies have demonstrated that protection from light is not necessary for the E7389 drug product.

11.1.5 Metabolism

Cytochrome 3A4 (CYP3A4) appears to be the major enzyme responsible for the human hepatic metabolism of E7389, and forms mainly isomeric monohydroxylates in vitro.

11.1.6 Preparation & Administration

Aseptically withdraw the required amount of HALAVEN from the single-use vial and administer undiluted or diluted in 100 mL of 0.9% Sodium Chloride Injection, USP. **Do not dilute in or administer through an intravenous line containing solutions with dextrose.** Do not administer in the same intravenous line concurrent with the other medicinal products. Store undiluted HALAVEN in the syringe for up to 4 hours at room temperature or for up to 24 hours under refrigeration (40°F or/ 4°C). Store diluted solutions of HALAVEN for up to 4 hours at room temperature or up to 24 hours under refrigeration. Discard unused portions of the vial.

11.1.7 Side Effects

The most common adverse reactions ($\geq 25\%$) reported in patients receiving eribulin were neutropenia, anemia, asthenia/fatigue, alopecia, peripheral neuropathy, nausea, and constipation. The most common serious adverse reactions reported in patients receiving eribulin were febrile neutropenia (4%) and neutropenia (2%). The most common adverse reaction resulting in discontinuation of eribulin was peripheral neuropathy (5%). Because clinical trials are conducted under widely varying conditions, the adverse reaction rates observed in the clinical trials of a drug cannot be directly compared to rates in other clinical trials and may not reflect the rates observed in clinical practice. In clinical trials, eribulin has been administered to 1,222 patients with multiple tumor types, including 240 patients exposed to eribulin for 6 months or longer. The majority of the 1,222 patients were women (82%) with a median age of 58 years (range: 26 to 91 years). The racial and ethnic distribution was Caucasian (83%), Black (5%), Asian (2%), and other (5%). The adverse reactions were identified in 750 patients treated in Study 1 [*see Clinical Studies (14)*]. In Study 1, patients were randomized (2:1) to receive either eribulin (1.4 mg/m² on Days 1 and 8 of a 21-day cycle) or single agent treatment chosen by their physician (control group). A total of 503 patients received eribulin, and 247 patients in the control group received therapy consisting of chemotherapy [total 97% (anthracyclines 10%, capecitabine 18%, gemcitabine 19%, taxanes 15%, vinorelbine 25%, and other chemotherapies 10%)] or hormonal

therapy (3%). The median duration of exposure was 118 days for patients receiving eribulin and 63 days for patients receiving control therapy. Table 2 reports the most common adverse reactions occurring in at least 10% of patients in either group.

11.1.8 Nursing Implications

There are no premedications required for eribulin infusion and eribulin is not a significant vesicant.

11.2 PLX3397

11.2.1 PLX3397 Administration

PLX3397 will be administered orally using a capsule formulation (200 mg per capsule). PLX3397 will be administered only to patients who have signed and dated an informed consent form. PLX3397 will be administered on a 5 day on, 2 day off schedule, repeated weekly, beginning C1D1 (baseline) for Phase Ib, or Day -7/-6 for Phase II. PLX3397 should be taken orally with 240 mL (8 oz) of room-temperature water in the fasting state. **The patient should fast at least 1 hour before administration and 1 hour after administration of PLX3397.** Patients will be permitted to eat a low-fat, bland snack (e.g., crackers, toast, tea) during the fasting period if needed. PLX3397 should be taken by the patient at approximately the same time of day.

Instructions for BID Dosing:

The time between BID doses should be approximately 12 hrs. Dosing may occur once daily (QD) under certain circumstances (e.g. dose reductions) and at the discretion of the Investigator in consultation with the Principal Investigator.

On C1D1, C1D2 and C2D1, the patients should take the morning dose of PLX3397 at the clinical site after the pre-dose PK blood sample is obtained— patients should be instructed not to take the study drug at home prior to these clinic visits. The time of dosing will be recorded in the clinic. The evening dose of PLX3397 should be taken by the patient at home. On all other visit days, patients may administer the study drug at home and record dosing information in the PLX3397 administration diary.

Missed doses of greater than 2 hrs before or after the appropriate dosing time should be skipped and not taken as a double dose at the next dosing timepoint. For example, a patient who takes their PLX3397 at 8 a.m. and 8 p.m. each day should not take their dose if they are outside of the ± 2 hr window period.

Patients who vomit their dose should be instructed to NOT make up that dose.

11.2.2 PLX3397 Packaging and Labeling

PLX3397-HCl capsules (200 mg strength of the active free base of PLX3397) are manufactured, packaged, and labeled according to GMP and GCP at the following address:

11.2.3 PLX3397 Storage and Stability

PLX3397-HCl capsules will be stored at the clinical site, as indicated on the study drug label, i.e., room temperature (between 15-30°C, or 59-86°F).

Patients will be requested to store PLX3397 at the recommended storage conditions noted on the label, out of the reach of children or other cohabitants.

11.2.4 PLX3397 Accountability, Reconciliation, and Return

The investigator is accountable for all test article supplied by the Sponsor. Copies of the completed source dispensing and inventory record(s) will be returned to the Sponsor (or designee) after the Sponsor (or designee) has performed accountability procedures. PLX3397 accountability will also be captured in the EDC throughout the course of the trial.

All PLX3397 capsules must be returned to the contract distribution center with the appropriate form if there is evidence that the product has been tampered within transit. Returned and unused PLX3397 capsules may also be destroyed and documented at the investigative site in accordance with GCP.

11.2.5 PLX3397 Compliance

At each clinic visit, patients will be questioned about their PLX3397 compliance. PLX3397 compliance will also be tracked through a patient diary.

12.0 Statistical Considerations

12.1 Endpoint Definitions

Phase I

The study will follow a standard dose-escalation schema (Phase Ib portion) with 3 to 6 patients per cohort (3+3 design). The starting dose level will consist of PLX3397 600 mg. Enrollment to successive cohorts up to dose Level 2 will be performed according to the table shown below, to establish the MTD. If 2 or more dose-limiting toxicities (DLTs) are observed at level 0, one dose reduction (to Level -1) is built in to the study design. All patients at a given dose level will be followed on treatment for at least 3 weeks before accrual to the next cohort can commence. There will be no intra-patient dose escalation allowed. For any dose cohort, if a patient is removed from study for reasons that are clearly not treatment-related, then an additional patient will be accrued to that dose level.

Dose Escalation Schedule		
Dose Level	Dose	
	PLX3397	Eribulin

Dose Escalation Schedule		
Level -2	400 mg (200 mg BID)	0.7 mg/m ² , 2-5 min IV Day 1, 8 q21 days
Level -1	400 mg (200 mg BID)	1.1 mg/m ² , 2-5 min IV Day 1, 8 q21 days
Level 0 (starting dose)	600 mg (400 mg AM; 200 mg PM)	1.4 mg/m ² , 2-5 min IV Day 1, 8 q21 days
Level 1	800 mg (400 mg BID)	1.4 mg/m ² , 2-5 min IV Day 1, 8 q21 days
Level 2	1000 mg (600 mg AM; 400 mg PM)	1.4 mg/m ² , 2-5 min IV Day 1, 8 q21 days

Phase II

The Phase II portion will begin after MTD is determined and we will enroll a total of 56 patients with TNBC to evaluate the safety and efficacy of the proposed treatment. Patients will be treated until clinical or radiographic disease progression or cumulative toxicity. Patients will be evaluated regularly in clinic with history, physical examination, and CT scans every 6 weeks. Visits will take place weekly during the first cycle (one cycle = 21 days) of study treatment, and then on day 1 and 8 of every 3 week cycle during the second cycle and beyond.

For Phase II, sample size is based under the Simon's 2-stage optimal design for progression-free survival at 3 months as a single proportion. The study is designed to determine the following hypothesis with >80% power and 2-sided type I error of 5% using binomial approximation: H₀: PFS% <39% versus H_a: PFS% > 57% (with PLX3397), where PFS% is the proportion of progression-free (PFS) at 3 months. The PFS% of >57% would represent a clinically relevant improvement with the treatment in triple-negative patients with locally recurrent or metastatic breast cancer. Based on these considerations, a sample size of 51 evaluable patients is required for the study. We plan for a targeted enrollment of 56 patients with 10% dropout rate.

Interim assessment and stopping rules for Safety and efficacy

Safety and SAE data will be routinely monitored. Because of the possibility of unacceptable or excessive defined serious adverse events during treatment or the study enrollment period, stopping rules for safety/tolerability are also developed. We have set the maximum rate of treatment-related SAE at 15% in patient enrollment. Thus, we may consider terminating the study if the number of patients with SAE is greater than the number expected under the binomial distribution. The following table shows the early stopping guideline based on the number of SAE observed under the rate of unacceptable SAE in the group sequential enrolment for the study. For example, assuming the unacceptable rate of SAE is greater than 15%, if the study observes 3 or more SAE in the first 17 treated patients, then we may consider if the study should be stopped early.

Safety Stopping Rules:

Number of enrolled patients with excessive SAE to consider early study termination.

Number patients in study	1-17	18-29	30-41
Unacceptable SAE – 15%	3	4	6

Efficacy Stopping Rules

Failure to obtain early responses at the scheduled tumor assessments will be taken as evidence that the regimen in question is ineffective. If fewer than 8 out of the first 20 pts are progression-free at 12 weeks, this would be considered an unacceptably low PFS rate (<39%), the study will not continue and accrual will cease. Accrual will continue while efficacy data is being determined. If 25 or fewer pts are progression free at 12 weeks at full accrual, then the treatment would be deemed ineffective. If the true PFS rate at 12 weeks is 39% for TNBC pts, the probability of terminating the study during the interim evaluation is 0.63; if the true PFS rate is 57% for TNBC pts, the probability that the trial will be stopped in the first stage is 0.10.

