12.2 Analysis Plan

Primary Efficacy Endpoint

Demographics and Baseline Characteristics

Demographic data (age, sex, race, ethnicity, body weight) and baseline disease characteristics will be tabulated and summarized and presented in data listings.

Progression Free Survival

Progression-free survival at 3 months (PFS) is defined as the proportion of patients alive and progression-free 90 days after Study Day 1. Duration of PFS is defined as the time from Study Day 1 to the earlier of disease progression or death due to any cause.

Progression free survival will be calculated from the first administration of PLX3397 with eribulin. The analyses of PFS will be performed using the Per Protocol population. These analyses are designed to include only objective progression events per the RECIST v1.1 criteria. Patients who do not have any post-baseline tumor assessments will be right censored on the date of Study Day 1. Patients who receive subsequent anti-cancer therapy before experiencing an event will be right censored at the date of the last tumor assessment prior to the date of initiation of subsequent therapy. Patients who have not experienced an event (and are not otherwise censored) at the time of data cutoff will be right censored on the date of their last tumor assessment

PFS will be estimated as a simple proportion based upon the results of the 12-week tumor assessment. Patients for whom this assessment is not performed will be included as failures, even if known to be alive at this timepoint. Confidence intervals will be provided. PFS and duration of PFS will also be estimated using Kaplan-Meier methods with associated confidence intervals.

Secondary and Supportive Efficacy Endpoints

Objective Response Rate

The objective response rate (ORR) is defined as the proportion of patients for whom the best overall response at the time of data cutoff is confirmed CR or confirmed PR as assessed per RECIST v 1.1 criteria. A table defining the derivation of best overall response to be applied will be provided in the SAP.

The analysis of ORR will employ the Per Protocol population. Patients who do not have any post-baseline tumor assessments will be counted as non-responders.

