12.3 Accrual Objectives

Phase I

A minimum of 12 patients will enroll in the Phase I trial, following a 3+3 design for 3 cohorts. We estimate that 10 patients will enroll at UCSF, and 7 patients each at Duke and Vanderbilt. Phase I completed at UCSF with 28 patients enrolled as 03/10/2015

Phase II

This study will enroll 56 patients (n=22 in the first stage and n=34 in the second stage) in the Phase II portion with the assumed 10% dropouts. We estimate that 26 patients will enroll at UCSF and 15 each at Vanderbilt and Duke.

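### The phase II type I error is labelled 2-sided 5%, but the decision rule is a one-sided test at about 5% (exact 0.048 to 0.054 with 51 evaluable patients)

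*Combined protocol and SAP*

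**What the plan says.** Section 12.1 (Endpoint Definitions, Phase II) states that "sample size is based under the Simon's 2-stage optimal design for progression-free survival at 3 months as a single proportion". The null is a 3-month progression-free proportion below 39% and the alternative is above 57%. The hypotheses are to be tested "with >80% power and 2-sided type I error of 5% using binomial approximation", from which the section concludes that "a sample size of 51 evaluable patients is required for the study". Enrolment is set at 56 to allow for 10% dropout.

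The Efficacy Stopping Rules in 12.1 stop the trial if fewer than 8 of the first 20 patients are progression-free at 12 weeks. For the end of the trial they say "If 25 or fewer pts are progression free at 12 weeks at full accrual, then the treatment would be deemed ineffective". If the true rate is 39%, "the probability of terminating the study during the interim evaluation is 0.63"; if it is 57%, the stated early-stop probability is 0.10.

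Three other places bear on the rule:

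- Section 10.1 repeats the stop at fewer than 8, but the same bullet ends by continuing to stage 2 "if at least 7 patients in the first stage of the phase II study are free of progressive disease at 12 weeks".
- Section 12.3 says "This study will enroll 56 patients (n=22 in the first stage and n=34 in the second stage").
- Section 12.2, on patients without the 12-week tumor assessment: "Patients for whom this assessment is not performed will be included as failures".

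**The concern.** A 2-sided 5% test puts 0.025 in each tail. The rule in 12.1 has no lower rejection region, and no 0.025 upper-tail level appears anywhere. The hypotheses point one way and so does the rule, so whatever error it carries is the risk of declaring benefit when the rate is really 39%.

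This is the primary endpoint of a single-arm trial, so the stated error rate is what tells a reader how far to trust a positive result. If the label is wrong, the risk in the direction of benefit is about twice what it implies. If the label is right, the power claim for 51 patients cannot be.

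**Working it through.** **Inputs.** From 12.1: p0 = 0.39, p1 = 0.57, n1 = 20, N = 51, so 31 patients in stage 2. Success means 26 or more progression-free. The stage 1 stop is at r1 or fewer, where r1 is:

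- 7 from the wording of 12.1 and the first part of the 10.1 bullet (fewer than 8);
- 6 from the last sentence of that bullet (7 continues);
- whatever value the stated 0.63 and 0.10 imply.

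**Formulas** (exact binomial)

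- Early stop: P(X1 ≤ r1), X1 ~ Bin(20, p).
- Declaring success: sum over x = r1+1 to 20 of P(X1 = x) × P(X2 ≥ 26 − x), X2 ~ Bin(31, p).

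The second expression is the type I error at p = 0.39 and the power at p = 0.57.

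**Step 1: reproduce the plan's figures**

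| Stop at | Early stop, p = 0.39 | Early stop, p = 0.57 |
|---|---|---|
| ≤ 6 | 0.280 | 0.014 |
| ≤ 7 | 0.452 | 0.040 |
| ≤ 8 | 0.631 | 0.096 |
| ≤ 9 | 0.784 | 0.195 |

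Only a stop at 8 or fewer returns the stated 0.63 and 0.10.

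**Step 2: error and power of the rule, N = 51, success at 26 or more**

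| Stop at | Source of boundary | One-sided error | Power |
|---|---|---|---|
| ≤ 8 | implied by 0.63 and 0.10 | 0.0483 | 0.801 |
| ≤ 7 | fewer than 8, in 12.1 and 10.1 | 0.0527 | 0.831 |
| ≤ 6 | at least 7 continue, in 10.1 | 0.0544 | 0.841 |

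With a stop at 8 or fewer, the 51 patients, power above 80%, 0.63, 0.10 and an error below 5% all fit together, provided the 5% is one-sided.

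**Step 3: take the 2-sided label literally (upper tail at most 0.025)**

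- Raising the final success cut-off to 27 of 51 leaves the error at 0.0275, 0.0293 or 0.0299 for stops at 8, 7 or 6. A cut-off of 28 brings it to about 0.015, with power 0.65 to 0.67.
- Over all stage 1 and final boundaries with n1 = 20 and N = 51, the best power is 0.685 (stop at ≤ 9, success at ≥ 27, error 0.0238).
- Allowing any n1 with N = 51, the best is 0.725. It needs 47 of the 51 patients in stage 1, so it is a bound rather than a practical design.
- The smallest two-stage design with error at most 0.025 and power at least 0.80 has 61 patients (n1 = 36, stop at ≤ 14, success at ≥ 32: 0.0224 and 0.8001). The optimal design has 69 (n1 = 25, stop at ≤ 11, success at ≥ 35: 0.0247 and 0.8004).

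**Step 4: dependence on the denominator**

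The figures in Step 2 need exactly 51 patients. Keeping the cut-off of 25 and n1 = 20, with a 39% rate for every patient counted:

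| Patients counted | Error (stop at ≤ 8 to stop at ≤ 6) |
|---|---|
| 52 | 0.060 to 0.069 |
| 53 | 0.073 to 0.086 |
| 54 | 0.088 to 0.106 |
| 55 | 0.103 to 0.128 |
| 56 | 0.120 to 0.152 |

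The opposite case, as an assumption: all 56 are counted and 10% of them are failures through missing assessments. The effective rates are 0.9 × 39% = 35.1% and 0.9 × 57% = 51.3%. Error is then 0.039 to 0.051 and power 0.69 to 0.79.

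**The case against.** The strongest reply is that this is a slip of wording. The hypotheses are directional, the rule has only an upper success boundary, and the sample size, power and early-stop probabilities all reproduce at one-sided 5%. On that reading the go/no-go count of 26 does not move, no patients are added, and section 12.2 specifies no p-value that the label would alter. An exact error of 0.053 or 0.054 is also a small excess over a nominal 5% in a design that says it uses a binomial approximation. Much of this stands: one-sided 5% is the better-supported reading, which limits the matter to a correction. It does not remove the mismatch, because the stated error rate is still wrong for the rule.

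A second reply is that the stage 1 boundary and the denominator are separate defects, and that the denominator scenarios are extreme. Section 12.1 ties the requirement to 51 evaluable patients, section 12.2 uses the Per Protocol population, and section 12.6 replaces some patients who leave early for reasons other than progression or toxicity. This is fair as to size: 0.12 to 0.15 arises only if all 56 are counted against an unchanged cut-off. But replacement can also carry the evaluable number past 51, and the rule itself refers only to full accrual. The two points belong here because no corrected error rate can be written down until the boundary and the denominator are fixed.

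**Conclusion.** The concern holds. The rule in 12.1 is a one-sided test with an exact error of 0.048 to 0.054 and power of 0.80 to 0.84, depending on which stage 1 boundary applies. It is not a 2-sided 5% test with 0.025 in the upper tail. These figures assume n1 = 20, 51 patients in the final count and success at 26 or more.

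The documents do not say which error was intended, though their other numbers fit one-sided 5%. If so, this is a labelling error. If 0.025 in the upper tail was intended, power above 80% is unattainable at 51 patients. Either the label or the power claim must change. It should be corrected before the primary analysis, so that sidedness is not settled after the data are seen.

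**What to change.** 1. Reconcile the stage 1 boundary across section 10.1, the wording in section 12.1, and the stated 0.63 and 0.10.
2. State in 12.1 that the final cut-off of 25 applies to 51 evaluable patients, and what is done if more than 51 are evaluable.
3. State which error was meant.
   - If one-sided: replace the 2-sided label with the exact one-sided error and power of the reconciled boundary, namely 0.048 and 0.80 (stop at 8 or fewer), 0.053 and 0.83 (7 or fewer), or 0.054 and 0.84 (6 or fewer).
   - If 0.025 in the upper tail: withdraw the claim of more than 80% power and restate power for the changed cut-off, or re-derive the sample size.
4. Make any interval reported for the primary endpoint consistent with the test stated. Its method is the sponsor's choice.

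**Cost.** If one-sided is confirmed, the change is wording in 10.1 and 12.1 and no extra patients. The price is a less favourable stated error, slightly above 5% if the stop is at 7 or fewer or at 6 or fewer. Keeping both 0.025 and 80% power would need at least 61 − 51 = 10 more evaluable patients.

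### The interim futility rule as written (stop below 8 of 20) does not have the stated stopping probabilities of 0.63 and 0.10, and Section 10.1 both stops and continues the trial at exactly 7

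*Combined protocol and SAP*

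**What the plan says.** Section 12.1 (Efficacy Stopping Rules) stops the Phase II portion "If fewer than 8 out of the first 20 pts are progression-free at 12 weeks" and describes such a result as a rate below 39%. It then gives the rule's operating characteristics. At a true rate of 39%, "the probability of terminating the study during the interim evaluation is 0.63"; at a true rate of 57%, "the probability that the trial will be stopped in the first stage is 0.10". The final rule is in the same paragraph: "If 25 or fewer pts are progression free at 12 weeks at full accrual", the treatment is judged ineffective. The sample-size paragraph of 12.1 names Simon's two-stage optimal design and concludes that "a sample size of 51 evaluable patients is required for the study".

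Section 10.1 repeats the stop rule of fewer than 8 of the first 20, with the same 39% gloss. Two sentences later it says that accrual goes on to the second stage "if at least 7 patients in the first stage of the phase II study are free of progressive disease at 12 weeks".

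Section 12.3 gives the enrolled numbers as 22 in the first stage and 34 in the second, allowing for 10% dropout.

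**The concern.** This is the trial's only interim efficacy decision, and the text implies three different cut-offs for it:

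- 6 or fewer, from the continue clause in 10.1;
- 7 or fewer, from the stop clause in 10.1 and 12.1;
- 8 or fewer, from the stated probabilities.

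The first consequence is that anyone relying on 12.1 believes an ineffective regimen is stopped early 63% of the time, when the written rule does less. The second is that at 7 progression-free patients the decision depends on which sentence of 10.1 is followed, and at 8 the written rule and its quoted properties disagree. If either result occurs, the choice of rule would be made after the data are seen.

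**Working it through.** **Inputs.** First-stage size 20, p0 = 0.39, p1 = 0.57, total 51 evaluable, and success if more than 25 are progression-free (all from Section 12.1).

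**Step 1: stopping probability.** With X ~ Binomial(20, p), a rule that stops at k or fewer has P(stop) = Σ C(20, x) pˣ (1 − p)²⁰⁻ˣ over x = 0, …, k.

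| Rule | Source | p = 0.39 | p = 0.57 |
|---|---|---|---|
| Stated figures | 12.1 | 0.63 | 0.10 |
| Stop at 8 or fewer | boundary that reproduces them | 0.631 | 0.096 |
| Stop at 7 or fewer | stop clause, 12.1 and 10.1 | 0.452 | 0.040 |
| Stop at 6 or fewer | continue clause, 10.1 | 0.280 | 0.014 |

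The plan's figures are reproduced only with 8 or fewer. For the written rule the gaps are 0.63 − 0.45 = 0.18 and 0.10 − 0.04 = 0.06, too large for rounding.

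**Step 2: other explanations.** A normal approximation for 7 or fewer of 20 gives 0.445 and 0.039 with continuity correction, and 0.357 and 0.023 without. Using the 22 enrolled patients, 7 or fewer gives 0.324 and 0.015. Over every first-stage size from 10 to 34 and every cut-off, only 8 of 20 rounds to both stated values.

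**Step 3: the contradiction.** Seven is fewer than 8 and is also at least 7. Reading the first stage as the 20 patients, P(X = 7) is 0.172 at 39% and 0.026 at 57%. P(X = 8), where the written rule and the stated probabilities part, is 0.179 and 0.056. The two disputed results together have probability 0.172 + 0.179 = 0.351 at 39%.

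**Step 4: overall error.** If the trial stops at r1 or fewer, P(success) = Σ P(X = x) · P(Y ≥ 26 − x), summed over x = r1 + 1, …, 20, with Y ~ Binomial(31, p).

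| Interim rule | One-sided alpha (0.39) | Power (0.57) |
|---|---|---|
| Stop at 8 or fewer | 0.0483 | 0.801 |
| Stop at 7 or fewer | 0.0527 | 0.831 |
| Stop at 6 or fewer | 0.0544 | 0.841 |
| No interim stop | 0.0550 | 0.844 |

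**Step 5: which boundary was probably meant.** Among two-stage designs with 51 patients, one-sided alpha at most 0.05 and power at least 0.80, 8/20 with 25/51 has the smallest expected size at 39%: 20 + (1 − 0.631) × 31 = 31.4. The next is 9/22, at 31.8. The written 7/20 exceeds the 0.05 limit. Expected size only ranks designs here. It assumes that accrual pauses at the interim, which this trial does not do. The gloss points the other way: 7/20 is 35%, below 39%, whereas 8/20 is 40%.

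**The case against.** The arithmetic is not in dispute; the other side can argue about inference and weight.

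- **Support from optimality is limited.** With the total size left free, the smallest expected size belongs to 9/21 with 27/56 (30.65), and 8/20 with 25/51 ranks fourth. This stands. The evidence for 8 or fewer is mainly the unique match to 0.63 and 0.10, and the sponsor's intent remains unproven.
- **The error level.** Section 12.1 calls its 5% two-sided, while the comparison above is one-sided. If 0.025 per side was meant, every boundary exceeds it and alpha does not separate them. This too stands, as a separate matter to align when alpha is restated. It does not affect the stopping probabilities.
- **The working rule can be identified.** Section 3.1.2 refers to the statistical section for the design, where the stop rule is clear and 10.1 repeats it; the clause with 7 is a lone outlier that does not mention 20. A team following Section 12 would stop at 7. That lowers the practical risk, but both sentences in 10.1 are current text and need reconciling.
- **Little is lost overall.** Compared with 8 or fewer, the written rule has higher power and wrongly stops an effective regimen less often. This is true. The fault lies in the stated properties and the contradiction, not in a large loss of error control.

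**Conclusion.** Both parts hold. The written rule stops an ineffective regimen (39%) with probability 0.45, not 0.63, and an effective one (57%) with probability 0.04, not 0.10. Section 10.1 gives opposite instructions at exactly 7. The likely cause is a computed boundary of 8 written down as fewer than 8, but the 39% gloss fits the written rule, so only the sponsor can say which was intended. The effect on overall error is minor: one-sided alpha 0.053 against 0.048, power 0.83 against 0.80.

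The results assume exact binomial outcomes in 20 first-stage patients, the 25 of 51 final limit, and a fully applied interim rule. It still must be fixed, because a decision threshold cannot be carried out at one plausible result and its published properties are wrong.

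**What to change.** Have the sponsor confirm the boundary, then use identical wording in 12.1 and 10.1:

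- **Option (a).** Stop if 8 or fewer of the first 20 evaluable patients are progression-free at 12 weeks, and continue only with at least 9. Keep 0.63 and 0.10. Remove or reword the 39% gloss in both sections, since 8/20 is 40%.
- **Option (b).** Keep fewer than 8 and the gloss. Restate the stopping probabilities as 0.45 and 0.04, state one-sided alpha 0.053 and power 0.83, and change the continue clause in 10.1 to at least 8.

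Under either option, delete the clause with 7 and state that the 20 are evaluable patients. That follows from 51 evaluable and the enrolled 22 + 34 = 56 with 10% dropout, so the 22 in Section 12.3 needs no change. When alpha is restated, align it with the two-sided label in 12.1.

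The cost is a wording amendment in two sections, with no added patients. Compared with the rule as written, option (a) lowers power from 0.83 to 0.80 and raises the chance of wrongly stopping an effective regimen from 0.04 to 0.10. Option (b) means stating a lower chance of stopping an ineffective regimen (0.45) and a one-sided alpha slightly above 0.05.
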